### **3.5. Blinding**

The physicians in charge of outcome evaluation will be blinded about the grouping of the patients. The trial statistician will also be blinded regarding the treatment code when he develops the statistical analysis plan and writes the statistical programs, which will be validated and completed using dummy randomization codes. The actual allocation will only be provided to the study team after lock of the database.

### **3.6. Sample Size**

The sample size was calculated based on the primary outcome. According to our 3 months pilot study, the change score of Hyperactivity/Impulsivity assessed by doctor version of SNAP-IV scale in Baduanjin practice group (N=23) was 3.52 with a standard deviation of 5.81. Based on the outpatient data among ADHD patients, the mean change score Hyperactivity/Impulsivity assessed by doctor version of SNAP-IV scale in regular physical exercise patients was 0.37 with a standard deviation of 3.72. We assumed that the difference in the mean change score between Baduanjin practice group and regular

physical exercise group was 3.1 a standard deviation of 5.8. So as to demonstrate superiority with 80% of power and a significance level of 0.05 (two-sided), at least 56 participants for each arm will be required. With an anticipated a drop-out rate of 5%, a total of 120 participants need to be randomized.

## 4. Analysis Consideration

### 4.1. Trial hypothesis

The hypothesis H0: “No difference in the change of Hyperactivity/Impulsivity score assessed by doctor version of SNAP-IV scale at 3th month between two groups.” will be tested against the alternative” H1: “The change of Hyperactivity/Impulsivity score assessed by doctor version of SNAP-IV scale at 3th month is different between two groups.”

### 4.2. Study population data sets

Two study populations will be considered in the analysis as follows:

#### *-Intent-to-Treat population*

Intent-to-treat (ITT) population will be defined at the moment the randomization is performed. This will be the primary analysis for the trial.

Participants will be excluded from the ITT analysis if the primary outcome is missing, forming a modified ITT population (mITT).

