### 2.2. Outcomes

#### 2.2.1. Primary outcome

Hyperactivity/Impulsivity score change assessed by doctor version of SNAP-IV scale at 3th month.

Time Frame: Baseline, 3th month after initiation of intervention

Type: repeated measured continuous variable

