### **2.2.2. Secondary outcomes**

(1) Hyperactivity/Impulsivity score change assessed by doctor version of SNAP-IV scale at 6th month.

Time Frame: Baseline, 6th month after initiation of intervention

Type: repeated measured continuous variable

(2) Hyperactivity/Impulsivity score changes assessed by parent version of SNAP-IV scale.

Time Frame: Baseline, 3th month and 6th month after initiation of intervention

Type: repeated measured continuous variable

(3) Changes of Scoring evaluation of the TCM symptoms.

Time Frame: Baseline, 3th month and 6th month after initiation of intervention

Type: repeated measured continuous variable

(4) Change scores of inattention and Oppositional Defiant Disorder (ODD) subscale assessed by doctor version of SNAP-IV scale.

Time Frame: Baseline, 3th month and 6th month after initiation of intervention

Type: repeated measured continuous variable

(5) Change scores of inattention and Oppositional Defiant Disorder (ODD) subscale score assessed by parent version of SNAP-IV scale.

Time Frame: Baseline, 3th month and 6th month after initiation of intervention

Type: repeated measured continuous variable

(6) The changes of Weiss Functional Impairment Rating Scale (WFIRS) score.

Time Frame: Baseline, 3th month and 6th month after initiation of intervention

Type: repeated measured continuous variable

(7) The changes of parent version of Achenbach Child Behavior Checklist (CBCL) score.

Time Frame: Baseline, 3th month and 6th month after initiation of intervention

Type: repeated measured continuous variable

(8) The changes of Child version of Achenbach Child Behavior Checklist (CBCL) score.

Time Frame: Baseline, 3th month and 6th month after initiation of intervention

Type: repeated measured continuous variable

(9) The changes of CANTAB test (neuropsychological tests) score.

Time Frame: Baseline, 3th month and 6th month after initiation of intervention

Type: repeated measured continuous variable

(10) The changes of BRIEF2 scale (ecological rating scale) score.

Time Frame: Baseline, 3th month and 6th month after initiation of intervention

Type: repeated measured continuous variable

(11) The changes of Visual Perception-2nd edition (DTVP-2) score.

Time Frame: Baseline, 3th month and 6th month after initiation of intervention

Type: repeated measured continuous variable

(12) The changes of Child Sensory Integration Checklist score.

Time Frame: Baseline, 3th month and 6th month after initiation of intervention

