## **5. Statistical Analyses**

### **5.1. Primary Outcome Analysis**

#### **5.1.1. ITT analysis of the primary outcome - the primary analysis**

The primary outcome is a repeated measured continuous variable, Hyperactivity/Impulsivity score change in doctor rated SNAP-IV scale. The primary analysis will be based on the mITT population as defined above. Generalized liner

mixed model (GLMM) will be performed using maximum likelihood (ML) method with treatment (binary) and time (ordinal) and interaction of treatment with time as fixed effect, and ID as random effect. Gaussian distribution and identity link function will be used in the GLMM model. Mean difference and 95% confidence intervals (CI) between groups at each time point will be estimated based on the fitted GLMM model.

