## **5.2. Secondary Outcome Analysis**

All secondary outcomes will be analyzed as for a superiority designed trial and two-sided significance with alpha=5% and standard 95% CIs for the treatment differences in these outcomes between two groups will be calculated and presented. Secondary outcome analyses will be based on the mITT population unless specified.

The continuous outcome such as weight will be summarized using number of subjects (n), mean, standard deviation (SD), minimum, and maximum by treatment group, and will be analyzed by a GLMM model. Mean differences with 95% confidence intervals between two groups will be derived from the GLMM model.

All the secondary outcomes would be analyzed in the same tactics of primary outcome described above.

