### **5.2.1. Handling of Missing data**

Missing baseline covariates will be imputed using simple imputation methods in the covariate adjusted analysis based on the covariate distributions, should the missing values for a particular covariate be less than 5%. For a continuous variable, missing values will be imputed from random values from a normal distribution with mean and SD calculated from the available sample. For a categorical variable, missing values will be imputed from random values from a uniform distribution with probabilities P1,

P2, ..., and Pk from the sample. The seed to be used is 20211215.

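### The SAP's mITT rule discards usable 6-month and secondary scores of children who lack only the 3-month clinician rating, and no sensitivity analysis covers a missing 3-month score

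*SAP*

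**What the plan says.** SAP 4.2 fixes the ITT population at randomisation and says of it "This will be the primary analysis for the trial". The next sentence narrows it: "Participants will be excluded from the ITT analysis if the primary outcome is missing, forming a modified ITT population (mITT". What counts as missing follows from SAP 2.2.1, where the primary outcome is "Hyperactivity/Impulsivity score change assessed by doctor version of SNAP-IV scale at 3th month".

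SAP 5.1.1, although headed as an ITT analysis, says "The primary analysis will be based on the mITT population as defined above". Its response is "Hyperactivity/Impulsivity score change in doctor rated SNAP-IV scale", fitted by maximum likelihood with treatment, time, their interaction and a random effect for child.

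For the other endpoints, SAP 5.2 says "Secondary outcome analyses will be based on the mITT population unless specified". The first of these in SAP 2.2.2 is "Hyperactivity/Impulsivity score change assessed by doctor version of SNAP-IV scale at 6th month". The parent-rated, TCM and other scales follow in the same list.

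Protocol 2.15.1 names the ITT population for the primary analysis and, unless specified, for the secondary ones. It plans a GLM at 3 months and refers to the SAP for detail.

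On missing data, SAP 5.2.1 says only: "Missing baseline covariates will be imputed using simple imputation methods in the covariate adjusted analysis". The remaining analyses of the primary outcome are per-protocol, covariate-adjusted and subgroup (SAP 5.1.2 to 5.1.4).

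**The concern.** Two things are at stake. First, inclusion in every default analysis depends on one particular measurement being present. A child who misses the 3-month clinician rating but attends at 6 months loses that 6-month clinician score, and the parent-rated, TCM and other scores as well. The SAP gives no reason why, say, a parent-rated scale should depend on a different rater's score at a different visit. Protocol 2.12.1 foresees quarantine disruption of visits, so this pattern of attendance is possible.

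Second, the comparison of retained children is unbiased only if loss is unrelated to outcome or acts alike in both arms. The data cannot confirm that, and nothing planned shows how far the result depends on it. The per-protocol set is defined by qualified exercise days, so it does not test the assumption. The adjusted and subgroup analyses run on the mITT and per-protocol sets and do not test it either.

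**Working it through.** **1. The plan's own figure.** Inputs from SAP 3.6: difference 3.1, SD 5.8, two-sided alpha 0.05, power 80%, drop-out 5%, total 120.
- The two-sample t-test needs 55.93, so 56 per arm, as stated. 112/0.95 = 117.9, so 118; 120 covers it.
- With 60 per arm and 5% lost (3 children), 57 per arm remain. SE = 5.8 × √(2/57) = 1.086. The smallest significant difference is 1.981 × 1.086 = 2.15. Power for 3.1 is 0.81.

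Power is therefore not the issue at the planned loss.

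**2. Whom the rule changes.**

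| Scores available | Effect of the SAP 4.2 rule |
|---|---|
| Baseline only | Excluded, but would add nothing to a change-score model or to the protocol's 3-month GLM |
| Baseline and 6-month clinician scores, no 3-month clinician score | Excluded; the 6-month score is lost although the ML model could use it under missing at random |
| Other scales present, no 3-month clinician score | Excluded from the analyses of those scales by default |
| 3-month clinician score present, 6-month missing | Retained; ML handles the gap under missing at random |
| Drop-out criterion met, 3-month score present | Retained |

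Only the second and third rows lose information. The documents do not say how many children would fall there.

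**3. Possible bias from informative loss.** Let p be the fraction lost in an arm and g the mean of the lost minus the mean of the retained. Within an arm, retained mean minus full mean is −p × g. For arm A minus arm B:

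bias = pB × gB − pA × gA

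This is zero if loss is alike in both arms. Suppose loss is informative in one arm only, with g between 3.1 (the planned effect) and 5.8 (one SD). Both gaps are assumptions, and the sign can go either way.
- 5% lost in each arm: 0.05 × 3.1 = 0.16 and 0.05 × 5.8 = 0.29 points. With SE 1.086, type I error is 5.2% and 5.8%.
- Assumed 10% v 5% (54 and 57 retained), informative in the 10% arm: 0.10 × 3.1 = 0.31 and 0.10 × 5.8 = 0.58 points. SE = 5.8 × √(1/54 + 1/57) = 1.101, so type I error is 5.9% and 8.2%.

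**4. How much of that is the rule's doing.** The rule's own effect is the gap between mITT and a change-score model on all available data. It was simulated with 60 per arm, no true difference, change SD 5.8 and an unstructured ML fit, with one arm losing children only from its worse-responding half and the other losing at random. Baseline SD 4 and correlations of 0.3 to 0.7 are assumptions.
- mITT bias was 0.23 to 0.25 points in size at 5%/5% loss and 0.50 to 0.52 at 10%/5%.
- Lifting the exclusion removed 0% of it if no lost child was seen at 6 months, 5–12% if half were, and 10–20% if all were.
- The rule's share is therefore at most about 0.20 × 0.25 = 0.05 points or 0.20 × 0.52 = 0.10 points.

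**5. What a delta analysis would show.** This ignores the extra variance from imputation.
- 5% loss: an observed 3.1 stays significant unless lost children in one arm differ by about (3.1 − 2.15)/0.05 ≈ 19 points, on a subscale of 0 to 27.
- 10% v 5% loss: the smallest significant difference is 2.18, and the shift needed in the 10% arm is (3.1 − 2.18)/0.10 = 9.2 points.
- Near the border a one-SD gap is enough. It would overturn an observed difference between 2.15 and 2.15 + 0.05 × 5.8 = 2.44 (5% loss), or between 2.18 and 2.18 + 0.10 × 5.8 = 2.76 (10% v 5%).

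**The case against.** The strongest reply is that SAP 4.2 only makes explicit what the protocol would do anyway. The protocol's GLM at 3 months, with no imputation stated, cannot use a child without a 3-month score, and Protocol 2.15.1 defers detail to the SAP. The ±4-week visit windows and the retention measures are there to keep such cases few, and at 5% loss the figures are small. For the primary 3-month test this largely stands. It does not answer the loss of data on the other endpoints or the lack of any check on missing 3-month scores.

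Three stronger readings are tempting, and the documents do not support them.
- A reader might infer that the mITT rule itself causes a bias of 0.16 to 0.58 points. It does not. That bias comes from informative loss and would mostly remain without the rule.
- A reader might see a plain contradiction with Protocol 2.5, which keeps data up to drop-out for analysis. That section does not say which analysis. Outcomes are measured only at enrolment, 3 and 6 months, so a child lost before month 3 has only baseline outcome scores to contribute.
- A reader might conclude that a child can be in the per-protocol set but not in the primary set. That rests on the per-protocol definition being silent about missing outcomes, which is weak ground.

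The version-history entry on multiple imputation is not evidence either way, because a change log describes superseded text.

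**Conclusion.** The point holds as a cheap improvement; it is not a threat to the trial's main result. The two documents name different populations, but for the primary 3-month test the difference is mostly one of label. The substantive defects are the needless loss of 6-month and secondary data from children who lack only the 3-month clinician rating, and the absence of a sensitivity analysis for a missing 3-month score.

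The only loss rate in the documents is 5%, and at that rate the possible bias is well below the planned effect. It would matter if loss were higher or unequal, or if the result fell near the significance border. The 10% v 5% loss, the gaps of 3.1 to 5.8 points and the simulation's baseline SD and correlations are assumptions. The direction of any bias is unknown.

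**What to change.** 1. Reconcile Protocol 2.15.1 with SAP 4.2, 5.1.1 and 5.2. Define the primary set as all randomised children, analysed as randomised, with every available post-baseline clinician score entering the ML mixed model of SAP 5.1.1. Keep mITT as a sensitivity analysis. State that a child with no post-baseline score contributes only through item 3.
2. Analyse each secondary outcome on all available data for that outcome, not conditional on the 3-month clinician score.
3. Add a delta or tipping-point analysis for missing 3-month scores, varied separately by arm (for example 0 to ±5.8 points), and report missingness by arm. This item matters most, because items 1 and 2 remove little of any bias from informative loss.

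Protocol 1.3 plans conduct to March 2022 and SAP version 2.0 is dated October 2022, so timing matters. If allocation has already been released under SAP 3.5, keep mITT as the specified primary analysis and report items 1 to 3 as sensitivity analyses added after unblinding.

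The cost is SAP wording, one extra sensitivity analysis and possibly slight dilution of the estimate. The sample size stays at 120.

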#### *-Per-protocol population*

Participants will be excluded from the per-protocol population if their qualified exercise days (more than 30 minutes and the maximum heart rate during the exercise should be over 120 beats) less than 48 days. The experimental group in the per-protocol analysis will be defined according to what the participant actual receive. This population will be used for the supportive analyses.

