2.5.2 Definition of adherence

Researchers will check the uploaded data every day. If the time of exercise exceeds 30 minutes, and the maximum heart rate during the exercise is over 120 beats per minute, it is recorded as a day that meets the adherence standard. For the participants in the Baduanjin group, the score automatically rated by the Baduanjin software should also exceed 77.5. We require the participants to meet the adherence standard for at least 5 days each week. Participants that finished less than 80% required days are defined as having poor adherence.

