2.12 Data collection and management

2.12.1 Plans for assessment and collection of outcomes

The outcomes will be collected at 3 months and 6 months after allocation. Considering the ongoing COVID-19 quarantine, we allow participants to finish the first outcome evaluation at 3 months \pm 4 weeks, and for the second outcome evaluation, 6 months \pm 4 weeks.

The research staff is required to receive a three-hour training session to ensure that they fully understand the protocol and standard procedures for the trial. The blinded physicians for evaluating the primary and secondary outcomes attend a one-hour training on the outcome assessment. All the research questionnaires and tests will be conducted at the Children's Hospital of Fudan University. Data will be collected with a case report form (CRF) and recorded in an ACCESS database. The description of study instruments is provided in the outcome part of this protocol. The demographic information of participants, including birth date, sex, height, weight, routine habit of exercise, and current drug use, are recorded on the CRF. The test record of CANTAB will be downloaded from the Cambridge cognition official website and automatically saved as an excel document. All data collected during the study will be kept in a locked room or protected research server. Back-ups in the study folder on this protected research server will be saved regularly (once per 3 months). Only the study team has access to these documents. To ensure this trial is applied consistently to high quality, the Clinical Trial Unit (CTU) of Children's Hospital of Fudan University will regularly monitor enrolment records, CRFs, informed consent, and data records.

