### **5.1.4. Subgroup analyses of the primary outcome**

Subgroup analyses will be performed for the primary outcome if each subgroup contains enough subject after stratification. We will stratify by sex (binary), categorized baseline medication usage (using medicine or not when enrolled, binary), qualified exercise days (less than 30/36/42/48 days, respectively, binary), categorized baseline exercise habit(binary), categorized baseline WFIRS score, and categorized baseline

SNAP score, respectively. (According to the scale rules, the continues variable will be transformed to the categorical variable.)

Subgroup analyses will be performed on both mITT and PP populations.

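### The SAP's per-protocol rule leaves out the software-score condition that the protocol sets for an adherent day in the Baduanjin arm

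*SAP*

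**What the plan says.** Protocol 2.5.2 defines adherence day by day. The test common to both arms is "If the time of exercise exceeds 30 minutes, and the maximum heart rate during the exercise is over 120 beats per minute". One arm has a further condition: "For the participants in the Baduanjin group, the score automatically rated by the Baduanjin software should also exceed 77.5". Five such days a week are required, and the cut-off is relative: "Participants that finished less than 80% required days are defined as having poor adherence".

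SAP 4.2 is the only place where a per-protocol population is defined. A day counts under "qualified exercise days (more than 30 minutes and the maximum heart rate during the exercise should be over 120 beats", and a participant is excluded when the total is below 48: "the maximum heart rate during the exercise should be over 120 beats) less than 48 days". The software score is not mentioned. Nor does the SAP say how 48 was obtained, or between which dates days are counted.

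The per-protocol population is labelled supportive. It is used for the per-protocol analysis of the primary outcome (SAP 5.1.2), and again beside the mITT population for the covariate-adjusted and subgroup analyses (SAP 5.1.3 and 5.1.4).

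**The concern.** The two documents give different definitions of a good exercise day, and the difference falls in one arm only. Duration and heart rate are asked of both groups and could be met by almost any vigorous activity. The software score is the only adherence criterion that shows a child actually performed the Baduanjin movements. Protocol 2.4.2 and 2.5.1 say that researchers check the software data for that purpose.

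SAP 4.2 also says that the experimental group in this analysis is defined by what participants actually received. Without the score, that is verified in the Baduanjin arm by a test that cannot tell Baduanjin from other exercise.

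At stake is what the per-protocol estimate means. A reader of the protocol would take it as the effect among children who practised Baduanjin adequately. Under the SAP it is the effect among children assigned to Baduanjin who were active for long enough. If movement quality matters to the effect, the two estimates can differ.

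**Working it through.** **1. The day definitions side by side.**

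| Condition | Protocol 2.5.2 | SAP 4.2 |
|---|---|---|
| Over 30 minutes | both arms | both arms |
| Maximum heart rate over 120 | both arms | both arms |
| Software score over 77.5 | Baduanjin arm only | absent |
| Participant-level cut-off | 80% of required days | 48 days |

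The first two rows agree. The third does not. The fourth has to be checked by arithmetic.

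**2. Does 48 days agree with 80%?** Inputs: 5 required days a week and the 80% threshold (Protocol 2.5.2), and a 3-month intervention (Protocol 2.4.2; SAP 3.3.1 and 3.3.2). Neither document gives 3 months in weeks, so 12 and 13 weeks are both shown as assumptions.

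Required days = 5 x weeks; threshold = 0.80 x required days; implied adherence = 48 / required days.

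- 12 weeks: 5 x 12 = 60; 0.80 x 60 = 48; 48/60 = 80.0%. The SAP figure is reproduced exactly.
- 13 weeks: 5 x 13 = 65; 0.80 x 65 = 52; 48/65 = 73.8%.

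SAP 5.1.4 points to the 60-day base. Its cut-offs, "qualified exercise days (less than 30/36/42/48 days, respectively, binary", divided by 60 give 30/60 = 50%, 36/60 = 60%, 42/60 = 70% and 48/60 = 80%. Divided by 65 they give 46%, 55%, 65% and 74%. The round percentages make 12 weeks the likely origin, although the SAP does not say so.

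**3. What the missing score does.** Take the 60-day base and read the 77.5 condition as applying to each day, which is the natural reading because it follows directly on the definition of an adherent day. Consider, for illustration, a Baduanjin child with 50 days that pass on time and heart rate, of which 40 also score above 77.5.

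- SAP: 50 is at least 48, so the child is per-protocol.
- Protocol: 40/60 = 67%, below 80%, so the child is poorly adherent.

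The same child is classified in opposite ways. This holds for any Baduanjin child with at least 48 days on the SAP definition but fewer than 48 on the protocol's. It cannot happen in the control arm, where the day definitions are identical.

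**The case against.** The best defence is that the omission may be deliberate. The protocol defines adherence but no per-protocol population, so the SAP is free to choose one. The same time and heart-rate test in both arms is defensible: a score threshold would select on performance in the Baduanjin arm with no counterpart among controls, and could favour that arm if better performers also improve more. This stands as a reason not to replace one definition with the other. It does not remove the problem, because the SAP neither acknowledges nor explains the departure.

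The analysis is also only supportive, and the covariate-adjusted and subgroup analyses are run on the mITT population too. That stands, and it limits the consequence.

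A reader might go further and infer that the 48-day count itself contradicts the protocol, or that it means widely varying adherence because of the visit window ("we allow participants to finish the first outcome evaluation at 3 months", plus or minus 4 weeks). Taking 3 months as 13 weeks and counting required days up to the visit gives 48/45 = 107% at week 9 and 48/85 = 56% at week 17. The documents do not support this. The window is stated for study visits and outcome evaluation (Protocol 2.5 and 2.12.1), whereas the exercise period is fixed at 3 months. Protocol 2.6.1 says that both arms have completed 3 months by the primary rating.

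It is equally tempting to say that the rule removes adherent children who are rated early, or that it counts exercise done after the outcome. These are alternative readings of a text that gives no counting dates, and neither is what the SAP says.

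**Conclusion.** The point holds for the day definition. SAP 4.2 omits a condition that Protocol 2.5.2 imposes in the Baduanjin arm, so children whom the protocol calls poorly adherent can enter the per-protocol population in that arm only. The number affected, and the direction of any effect on the estimate, cannot be derived: the documents give no score distribution and no evidence linking score to outcome. The conclusion assumes that the score applies day by day.

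The day count is not a contradiction. It equals the protocol's 80% if 3 months is 12 weeks and is 74% if it is 13; with a fixed 3-month period, that is the whole supportable range. The unstated base and counting dates are missing detail to be supplied along with the correction.

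The primary mITT analysis is untouched. This is a matter to settle in the SAP before the per-protocol results are interpreted.

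**What to change.** Reconcile SAP 4.2 with Protocol 2.5.2, without treating either definition as the right one:

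1. Run the supportive per-protocol analysis twice: once with the current time and heart-rate definition, and once with the protocol's full definition including the 77.5 score in the Baduanjin arm. Show both, and give the number of children by arm who enter under each.
2. State that 48 is 80% of 5 x 12 = 60 days.
3. State that only days within the 3-month intervention and before the 3-month rating are counted.
4. Add the qualified-day count under each definition to the SAP's section 7 variable list, where neither that count nor the software score is visible.

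Keep the fixed count. A denominator that moved with the visit date would admit a child rated at week 9 with 36 qualified days (36/45 = 80%), although that is only 36/60 = 60% of a 12-week course.

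The cost is SAP wording, the derived variables and one extra supportive run; tracker and software data are already uploaded. There are two downsides. The score selects on performance in one arm only, which is why both versions are needed. And once counting stops at the rating, a child doing exactly 5 days a week needs 48/5 = 9.6 weeks to qualify, so anyone rated earlier at that pace drops out. The number excluded for that reason should be reported by arm.
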